3.3 Visit 2 Pre-Randomization

The patient will return after a twelve-hour fast and avoidance of alcohol for 24 hours. Vital signs will be obtained. Blood will be obtained for DNA, C4, FGF-19 and pk analysis. Blood will be obtained for routine safety labs of hematology, chemistry, lipid panel if patient did not have them on Visit 1 Screen. Urine will be obtained for a pregnancy test for females of child-bearing potential.

Visit 2 may be combined with Visit 3 for greater convenience if requested by patient.

3.4 Visit 3 Randomization

Vital signs will be obtained. The patient will be asked about any changes in eligibility criteria, concomitant medications and adverse events. The patient will bring in a single, random stool sample and will be given a new stool collection kit to bring in a sample at the next visit. The patient will return the bowel pattern diary

and receive a new bowel pattern diary. Study medication, either aldafermin or placebo, will be dispensed. A nurse will demonstrate proper subcutaneous injection into the abdomen and observe the patient self-administer the first dose of the study medication. Dosing instructions and potential side effects will be reviewed. Patients will be instructed to self-administer aldafermin/matched placebo as a subcutaneous injection into the abdomen at home at a similar time each day, preferably in the evening, after dinner and before bed, for 4 weeks.

Aldafermin/placebo syringes will be equilibrated to room temperature prior to use; this requires about 15 to 30 minutes at room temperature. The aldafermin/placebo syringe must be self-injected within an hour of being removed from the refrigerator. If the syringe is left at room temperature for longer than an hour, it must be discarded into a provided red sharps container and a replacement syringe used. The aldafermin/placebo syringes are provided as kits with four additional syringes. Additional or replacement study medication syringes are available. Patients must record time of dosing in the bowel pattern diary.

3.5 Visit 4 Interim Treatment Testing

About two weeks later, the patient will return after a twelve-hour fast and avoidance of alcohol for 24 hours. The patient will be asked about any changes in eligibility criteria, study medication dosing, concomitant medications and adverse events. Vital signs will be obtained. The patient will turn in any remaining study medication and receive a new supply. The patient will bring in a single, random stool sample and will be given a new stool collection kit to bring in a sample at the next visit. The patient will return the bowel pattern diary and receive a new bowel pattern diary. Blood will be obtained for C4, FGF19 and pk analysis. Urine will be obtained for a pregnancy test for females of child-bearing potential.

3.6 Visit 5 End of Study Testing

About two weeks later, the patient will return after a twelve-hour fast and avoidance of alcohol for 24 hours. The patient will be asked about any changes in eligibility criteria, study medication dosing, concomitant medications and adverse events. Weight and vital signs will be obtained. The patient will have an interview and a brief physical exam by a study physician. The patient will be asked to complete the Quality-of- Life (QoL) questionnaire once more. Blood and urine will be obtained for routine safety labs of hematology, chemistry, lipid panel and a dipstick urinalysis. If there is a clinically significant change in any lab test result, the test will be repeated in 30 days' time to ensure the result has returned to pre-study medication levels. A 12-lead electrocardiogram (ECG) will be performed. The patient will return any remaining study medication. The patient will turn in a single, random stool sample. The patient will return the bowel pattern diary. Blood will be obtained for C4, FGF19 and pk analysis.

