4.2 Inclusion Criteria

Patients must meet ALL of the following inclusion criteria to be eligible for enrollment into the study:

1. Aged 18 to 75 years, inclusive at Visit 1 Screen.
2. Clinical diagnosis of functional diarrhea or IBS with diarrhea according to Rome III or IV criteria at Visit 1 Screen.
3. Clinical laboratory evidence of BAM (20-22), with at least one of the following results recorded in their past medical history:
 - Serum C4 \geq 52 ng/mL
 - Fecal BA $>$ 2337 μ moles / 48 hours
 - Total fecal BA $>$ 1000 μ moles / 48 hours + 4 % primary BA
 - Fecal primary BA $>$ 10% / 48 hours
4. Body mass index (BMI) 18.0 to 45.0 kg/m², inclusive at Visit 1 Screen
5. Understands the study procedures, is willing and able to comply with the study procedures, and is able to give informed consent
6. If treated with any of the following medications, dosing must be stable for 30 days prior to Visit 1 Screen. Patient must agree to maintain the same dose of medication throughout the study:
 - Tricyclic antidepressants, selective serotonin reuptake inhibitors (SSRIs) and serotonin and norepinephrine reuptake inhibitors (SNRIs).
 - Bile Acid sequestrants such as colestipol, cholestyramine and colestevam.
7. Patients must use one highly effective method of contraception for 30 days before the study through 90 days after study completion for males and through 30 days after study completion for females. Highly effective methods of contraception include
 - Oral, implantable, subdermal or injectable hormonal contraceptives
 - Standard intrauterine device or vaginal ring
 - Male or female condoms and diaphragms used with spermicide
 - Abstinence from heterosexual intercourse
 - Female partners exclusively sexually active with a surgically sterilized male partner
 - Females who are surgically sterile prior hysterectomy, bilateral salpingectomy, or bilateral oophorectomy) or postmenopausal (defined as: 12 consecutive months with no menses) are not considered to be of childbearing potential

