6. STUDY ASSESSMENTS AND PROCEDURES

6.1. Screening and Eligibility

Patient eligibility will be assessed based on protocol inclusion and exclusion criteria. All screening evaluations must be completed and reviewed to confirm potential patients meet all eligibility criteria.

Screening procedures must be completed within 28 days prior to initiation of study medication.

At the Visit 1 Screen or during the optional remote consent and eligibility review, potential patients will have a detailed verbal presentation of the nature, purpose, risks, and requirements of the study in addition to receiving detailed written information. Patients will have adequate opportunity to ask the appropriate person of the study team (ie, Principal Investigator or designee) about any aspect of the study. If a patient decides that he/she is willing to participate in the study, he/she will be asked to sign the informed consent form. The clinical personnel obtaining written consent from the patient will also sign the form to confirm consent has been obtained. Once signed, the original consent will be maintained for the study records and a signed copy given to the patient. A copy will be scanned into the patient's electronic medical record. The investigator will verify that informed consent has been obtained from each patient prior to the patient undergoing any study-related procedures.

Visit 1 Screen consists of:

- Complete medical history
- Physical examination, including height, weight, and vital signs (heart rate, blood pressure, temperature and respiration rate)
- Safety 12-lead ECG
- Clinical laboratory tests: The standard Comprehensive Metabolic Panel which includes calcium, creatinine, sodium, potassium, albumin, alkaline phosphatase, total bilirubin, carbon dioxide, chloride, glucose, total protein, BUN, AST, and ALT. Hematology includes a CBC with differential. A lipid panel including total cholesterol, HDL, LDL and triglycerides will be performed. Analysis of the urine will be completed by a standard urine dipstick method with microscopy.

- Urine human chorionic gonadotropin (hCG) pregnancy test (for females of childbearing potential)

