6.6 Clinical Laboratory Tests

Clinical safety laboratory tests will be performed at the study site at Visit 1 Screen or Visit 2 and Visit 5 End of Study. These tests include the Comprehensive Metabolic Panel, calcium, creatinine, sodium, potassium,

albumin, alkaline phosphatase, total bilirubin, carbon dioxide, chloride, glucose, total protein, BUN, AST, and ALT. Hematology includes a CBC with differential. A lipid panel including total cholesterol, HDL, LDL and triglycerides will be performed. Analysis of the urine will be completed by a standard urine dipstick method with microscopy. The investigator will the laboratory report, document the review, and record any clinically relevant changes as AEs.

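### Urine pregnancy testing stops at about Day 14: none is scheduled at Visit 5, and none at Visit 3 before the first dose when that visit is held separately from Visit 2.

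*Combined protocol and SAP*

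**What the plan says.** Sections of the combined protocol and SAP that bear on pregnancy testing:

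- **Screening (6.1).** A urine hCG for females of childbearing potential is on the Visit 1 list. The Visit 1 text in 3.2 does not repeat it. Timing is limited only by "Screening procedures must be completed within 28 days prior to initiation of study medication".
- **Visit 2 (3.3).** A urine pregnancy test is scheduled. The visit may be merged with the next: "Visit 2 may be combined with Visit 3 for greater convenience if requested by patient".
- **Visit 3 (3.4).** No pregnancy test is listed. The patient is asked about changes in eligibility, and a nurse will "observe the patient self-administer the first dose of the study medication".
- **Visit 4, about Day 14 (3.5).** "Urine will be obtained for a pregnancy test for females of child-bearing potential".
- **Visit 5, about Day 28 (3.6).** "Blood and urine will be obtained for routine safety labs of hematology, chemistry, lipid panel and a dipstick urinalysis". No pregnancy test is listed. The patient is asked about eligibility changes and adverse events, and has a physician interview and a brief examination.
- **Laboratory tests (6.6).** "Clinical safety laboratory tests will be performed at the study site at Visit 1 Screen or Visit 2 and Visit 5 End of Study". The list that follows has no hCG.

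Around this schedule, pregnancy is the first exclusion (4.3) and leads to immediate withdrawal from treatment (4.4). On contraception, 4.2 says "Patients must use one highly effective method of contraception for 30 days before the study", and for females this continues until 30 days after completion. Section 6.3 makes harm to a fetus or child after maternal exposure a serious adverse event. No later visit or post-treatment pregnancy test is described.

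**The concern.** The plan tests before dosing and again halfway through, then stops. A urine test cannot detect a conception until some days afterwards, so the Visit 4 test mainly reflects the period before dosing began. A woman who conceives in roughly the first half of dosing would usually test negative at Visit 4 and leave the study with no further test. Whether the exposed pregnancy is known then depends on her knowing of it and saying so. The serious adverse event category in 6.3 for fetal harm is hard to apply reliably to a pregnancy nobody knows about.

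A related gap lies at the start of dosing. The last pre-dose test is at Visit 2, and if Visit 3 is on a later day nothing confirms that the result still holds. What is at stake is safety follow-up and, for the Visit 3 gap, avoidable doses in early pregnancy.

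**Working it through.** The plan gives no figure to reproduce here. The check is a reading of each visit's test list followed by timing arithmetic.

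**Inputs from the documents**
- Visit 4 at about Day 14 and Visit 5 at about Day 28 (3.1, 3.5, 3.6).
- 15 patients per arm and 30 in total, with accrual of 36 (2.1, 7.2).
- 90% female anticipated (3.1).
- Screening window of 28 days (6.1).

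**Assumptions, not in the documents**
- Lag L from conception to a positive urine test: 14 days, range 10-18.
- Contraceptive failure: 1-10% per year.
- Every woman is of childbearing potential. The true share is not stated, and ages run to 75.

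**Step 1: conceptions each test can reach.** A test on Day T detects conceptions up to Day T − L.

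| L (days) | Visit 4 reaches (14 − L) | A Visit 5 test would reach (28 − L) | Share of Day 0-14 conceptions missed at Visit 4 but detectable at Visit 5 |
|---|---|---|---|
| 10 | Day 4 | Day 18 | (14 − 4)/14 = 71% |
| 14 | Day 0 | Day 14 | 14/14 = 100% |
| 18 | Day −4 | Day 10 | 10/14 = 71% |

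The gain is (28 − L) − (14 − L) = 14 conception days whatever the lag. The period still not reached runs from Day 28 − L to Day 28, which is the last L days of dosing: about 14 (10-18).

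**Step 2: expected yield of a Visit 5 test on the aldafermin arm.**
- Women: 0.9 × 15 = 13.5.
- Woman-years in the added 14 days: 13.5 × 14/365.25 = 0.517.
- Expected pregnancies: 0.517 × 0.01 to 0.517 × 0.10 = 0.005 to 0.05.
- If half the women are of childbearing potential: 0.003 to 0.03.

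**Step 3: expected yield of a Visit 3 test.** With a gap of g days between Visits 2 and 3, a test on Day 0 adds g conception days. Expected pregnancies are 13.5 × g/365.25 × (0.01 to 0.10).
- g = 0 (visits combined): 0.
- g = 7: 0.003 to 0.03.
- g = 28 (the full screening window): 0.01 to 0.10.

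Each such pregnancy would otherwise receive about 14 daily doses before the Visit 4 test.

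**Step 4: number of women to test, both arms.** 0.9 × 30 = 27 and 0.9 × 36 = 32.4, so about 27-33 women if all are of childbearing potential.

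**The case against.** The schedule can be defended as it stands. Its on-study tests come before drug is supplied: Visit 2 precedes the first dispensing, and Visit 4 is the resupply visit. Visit 5 dispenses nothing, and the only action the plan attaches to a pregnancy is stopping treatment, which by then is over. The Visit 5 questions cover pregnancy through the eligibility criteria, a physician sees the patient, and 6.3 captures fetal harm once it is known. The expected numbers are tiny and rest on outside assumptions.

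Much of this stands. A Visit 5 test prevents no dosing, and nothing in the plan is contradicted by leaving it out. What does not stand is treating the interview as equivalent to a test: a patient a few weeks past conception may not know. The methods accepted in 4.2 include user-dependent ones such as condoms and abstinence, so contraception reduces the risk without removing it.

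Three stronger readings are tempting and are not supported:
- *That a woman already pregnant could be dosed unnoticed for the whole study because Visit 3 has no test.* A pregnancy turning positive between Visits 2 and 3 would be picked up at Visit 4. The consequence is about 14 doses, and there is no gap when the visits are combined.
- *That the protocol commits itself to knowing every exposed pregnancy at exit.* Sections 4.3 and 4.4 are rules on eligibility and stopping, and 6.3 defines a serious event. A surveillance aim can be inferred from them but is not stated.
- *That a Visit 5 test would close the gap.* It would not reach conceptions in about the last 14 (10-18) dosing days.

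**Conclusion.** The gap is real on the visit text. No urine hCG is scheduled at Visit 5, and none at Visit 3 before the first dose. Over an assumed lag of 10-18 days, at least 71% of conceptions in the first 14 days of dosing would be missed at Visit 4 yet detectable at Visit 5; as planned, they are known at exit only by self-report.

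The size is very small: about 0.005-0.05 expected pregnancies on aldafermin for the Visit 5 test. For the Visit 3 test it ranges from 0 to 0.10 according to the gap, and the top figure needs the full 28-day window, 10% yearly failure and every woman being of childbearing potential. These figures are illustrations and should not be read as strict bounds, since 90% female is an expectation and accrual is set at 36.

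The reading is firm for the visit text. The schematic in 3.1 and the consent form were not available, and either could carry further pregnancy instructions. This is a minor point, a cheap improvement to safety monitoring with no effect on the efficacy analyses.

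**What to change.** - In 3.6, and in the Visit 5 list in 6.6, add a urine hCG for females of childbearing potential, run on the urine already collected.
- In 3.4, require a negative urine hCG before the first dose whenever Visit 3 is not on the same day as Visit 2.

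The cost is one or two urine tests per woman of childbearing potential, for about 27-33 women at the anticipated sex mix. The Visit 5 test needs no extra sample, and neither test needs an extra visit or any change to the analysis.

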3.7 Study Design Rationale

BAM/BAD is increasingly recognized as a subtype of IBS-D (11,27). In an open-label study (12), we identified beneficial effects of colestevam in the treatment of IBS symptoms in patients with high total fecal BA excretion ($> 2000\mu\text{moles}/48\text{h}$), elevated primary bile acids ($> 4\%$) with elevated total fecal bile acids ($> 1.000 \mu\text{mol}/48\text{h}$), or primary bile acids $> 10\% /48\text{h}$, elevated C4 ($> 40 \text{ ng/mL}$), and decreased FGF19 ($< 80 \text{ pg/mL}$).

4. STUDY POPULATION

4.1 Number of Patients

Approximately 36 patients with BAM/BAD irritable bowel syndrome-diarrhea will be enrolled.

4.2 Inclusion Criteria

Patients must meet ALL of the following inclusion criteria to be eligible for enrollment into the study:

1. Aged 18 to 75 years, inclusive at Visit 1 Screen.
2. Clinical diagnosis of functional diarrhea or IBS with diarrhea according to Rome III or IV criteria at Visit 1 Screen.
3. Clinical laboratory evidence of BAM (20-22), with at least one of the following results recorded in their past medical history:
 - Serum C4 \geq 52 ng/mL
 - Fecal BA $>$ 2337 μ moles / 48 hours
 - Total fecal BA $>$ 1000 μ moles / 48 hours + 4 % primary BA
 - Fecal primary BA $>$ 10% / 48 hours
4. Body mass index (BMI) 18.0 to 45.0 kg/m², inclusive at Visit 1 Screen
5. Understands the study procedures, is willing and able to comply with the study procedures, and is able to give informed consent
6. If treated with any of the following medications, dosing must be stable for 30 days prior to Visit 1 Screen. Patient must agree to maintain the same dose of medication throughout the study:
 - Tricyclic antidepressants, selective serotonin reuptake inhibitors (SSRIs) and serotonin and norepinephrine reuptake inhibitors (SNRIs).
 - Bile Acid sequestrants such as colestipol, cholestyramine and colestevam.
7. Patients must use one highly effective method of contraception for 30 days before the study through 90 days after study completion for males and through 30 days after study completion for females. Highly effective methods of contraception include
 - Oral, implantable, subdermal or injectable hormonal contraceptives
 - Standard intrauterine device or vaginal ring
 - Male or female condoms and diaphragms used with spermicide
 - Abstinence from heterosexual intercourse
 - Female partners exclusively sexually active with a surgically sterilized male partner
 - Females who are surgically sterile prior hysterectomy, bilateral salpingectomy, or bilateral oophorectomy) or postmenopausal (defined as: 12 consecutive months with no menses) are not considered to be of childbearing potential

4.3 Exclusion Criteria

Patients who meet ANY of the following exclusion criteria will not be eligible for enrollment into the study:

1. Pregnant or lactating
2. Structural or metabolic diseases/conditions that affect the gastrointestinal system
3. Use of the following medications at least 14 days prior to Visit 1 throughout the duration of the treatment period:
 - Patients may elect to withdraw from bile acid sequestrants such as colestipol, cholestyramine and colestevam or they may continue but they must continue at the same dose throughout the study.
 - GI medications including:
 - Anti-nausea agents including trimethobenzamide, promethazine, prochlorperazine, dimenhydrinate, hydroxyzine
 - Osmotic laxative agents including lactulose, sorbitol or PEG solutions as Miralax and Glycolax
 - Prokinetic agents including tegaserod, metoclopramide, prucalopride, domperidone, erythromycin, clarithromycin and azithromycin.
 - 5-HT3 antagonists including alosetron, ondansetron, tropisetron.
 - Patients may use Gabapentin if they are on a stable dose, which is not greater than 1200 mg a day.
 - Drugs with a known pharmacological activity at 5-HT4, 5-HT2b or 5-HT3 receptors including tegaserod, ondansetron, granisetron and tropisetron
 - All narcotics including codeine, morphine, and propoxyphene, either alone or in combination
 - Anti-cholinergics including dicyclomine, hyoscyamine, propantheline.
 - Antimuscarinics
 - Tramadol
 - Peppermint oil
 - Systemic antibiotics and antibiotics directed at colonic flora including rifaximin and metronidazole
5. Clinically relevant changes in dietary, lifestyle, or exercise regimen within 30 days prior to Visit 1 Screen and throughout the duration of the study
6. Any colonic or major abdominal surgery including bariatric surgery, gastric banding, stomach

surgery and intestinal or colonic surgery. Procedures such as appendectomy, cholecystectomy, hysterectomy, caesarean section, or polypectomy are allowed as long as they have occurred at least 3 months prior to Visit 1 Screen.

7. History of colorectal cancer, inflammatory bowel disease, diverticulitis, ischemic colitis, microscopic colitis or celiac disease
8. History of organic abnormalities of the GI tract, intestinal obstruction, stricture, toxic megacolon, GI perforation, or impaired intestinal circulation.
9. Other GI diseases such as GI bleeding or ulcerations
10. History of cerebrovascular disease including stroke, TIA, acute coronary syndrome, myocardial infarction or unstable angina
11. Clinically significant cardiac history or presence of electrocardiogram (ECG) findings at Visit 1 Screen:
 1. Abnormal heart rate < 40 or > 100 beats per minute
 2. QTc interval > 470 milliseconds (ms)
 3. QRS interval \geq 110 ms
 4. PR interval \geq 220 ms
12. Hepatic dysfunction including abnormal serum alanine aminotransferase [ALT] or aspartate transaminase [AST] $> 3 \times$ upper limit of normal [ULN]; total direct bilirubin $> 2 \times$ ULN, or alkaline phosphatase $> 2 \times$ ULN at Visit 1 Screen
13. Clinically significant renal insufficiency including serum creatinine > 2.5 mg/dL at Visit 1 Screen
14. History of severe head injury or history of seizures
15. History of suicide attempt or a hospitalization for a major psychiatric condition within 1 year prior to Visit 1 Screen. At Visit 1 Screen or during the optional remote consent and eligibility review, participants will complete the Hospital Anxiety and Depression questionnaire. If either score for anxiety or depression individually exceeds 8, the score will be discussed. The patient will be and advised whether to participate or whether to see their primary care physician.
16. History of alcohol use disorder or substance use disorder within 2 years of Visit 1 Screen.
17. Significant history or clinical manifestation of any endocrine, allergic, dermatological, hepatic, renal, hematological, pulmonary, GI, neurological or psychiatric disorder, malignancy (with the exception of treated basal cell carcinomas), or any other condition that would prevent the individual from participating in the study due to risk to the scientific validity of study assessments or to personal well-being of the patient.
18. Participated in another clinical study that includes an investigational drug or a biologic therapy within

30 days or 5 half-lives, whichever time period is longer, prior to Visit 1 Screen

